Penile vibratory stimulation mimics rapid and repetitive manual stimulation of the penis. Vibratory stimulation of the genitalia is considered safe by the medical community and offers potential benefits, such as treatment of orgasmic dysfunction, and improvement in ejaculatory and erectile function. Penile erection is controlled by spinal autonomic centers, the activity of which is dependent on input from supraspinal centers and genitalia. Penile erection is a culmination of successful nerve reflexes that initiate a penile vascular event. By activating the pudendo-cavernosal reflex, vibratory stimulation of the penis at high frequency can lead to a reflexogenic increase in penile blood flow. In addition, penile stimulation initiates a rhythmic contraction of the perineal muscles via the bulbocavernosus reflex, which subsequently produces erection rigidity.

The purpose of this study is to assess the ease of use, safety, and patient satisfaction of on-demand use of the Vibrect® device by men with mild to moderate erectile dysfunction. This research endeavor will be a phase I prospective trial exploring the use of a hand-held vibratory device for men with mild-to-moderate ED. The Viberet® device is Food and Drug Administration (FDA) approved for the use in men with ED, but limited studies have rigorously investigated the safety and patient effects of this device.

2. **Study Procedures**

This will be a single-center, prospective, phase I clinical trial. Subjects at JHMI will be recruited from the population of men who visit the urology outpatient clinics. Subjects who meet all study inclusions, and do not meet any study exclusions will be offered study participation. Patients will be referred to the study based on their initial clinic visit for ED consultation. We will not have any chart pre-screening and all the information gathered from a patient will be within the standard of care for their clinic consultation. Study eligibility will be determined from history and physical exam, response to validated erectile function questionnaires, and discussion on use of phosphodiesterase-5 (PDE-5) inhibitor and other medication use (dose, type, and need to obtain

successful penile erection). Should the patient wish to participate, the informed consent process will occur in a private clinic room and the patient will be given as much time as necessary to read and reflect upon the informed consent and all questions will be answered. No study procedures will be done prior to obtaining informed consent.

Those who wish to participate will sign an informed consent and will become familiar with the scope and protocol of the study. They will fill out the erectile function component of the international index of erectile function (IIEF-5), Erection Hardness Scale (EHS), Erectile Dysfunction Inventory of Treatment Satisfaction (EDITS), and Treatment Satisfaction Scale (TSS) questionnaires as a baseline. Patients will then be provided with a new Viberec stimulator and the manual, and will subsequently be instructed on the proper use of the device. Patients will demonstrate device use to ensure clarity with the explanation and instructions.

Prospective data will be collected from study subjects who will use the Viberec device. Men will be asked to perform vibratory stimulation of the penis while focused on sexual/erotic thoughts for approximately 7-10 minutes (depending on erectile response) for at least 3 times each week, at least 24 hours apart, throughout a four-week period. Men can perform the stimulation once daily, as long as each session is more than 24 hours apart. Men will record the frequency of device use, erectile response with stimulation, and whether they were able to achieve sexual satisfaction, which may include self-stimulation or penetrative intercourse.

Participants will fill out the IIEF-5, EHS, EDITS, and TSS questionnaires on week 4. The answers to these validated questionnaires will be compared to baseline to evaluate patient effect when using the device. The diaries will be evaluated to explore both the safety, as well as the patient effect when using the Viberec device.

If study subjects decide to use PDE-5 inhibitors during the 4-week study period (not provided by investigators), we ask that they record frequency of use, time, drug type, dosage, and commentary of sexual response as a result separately.

b. Study duration and number of study visits required of research participants.

The total duration of subject participation in this study is **4 weeks**. A total of 2 clinic visits will be included in this study. The first clinic visit will be the baseline evaluation and explanation of the study, and then a follow-up visit approximately 4 weeks after initiation of study period. This 4 week visit is standard of care visit, based on physician's discretion after starting a new therapeutic treatment of ED.

Initial visit: Perform the history and physical exam and to discuss the clinical study. Informed consent will be obtained at this visit if participant willing to proceed and meet inclusion criteria. Study subjects will fill out the IIEF-5, EHS, EDITS, and TSS for baseline documentation. Participants will receive their Viberec device, including the user manual (attached) and will receive instructions on the use of their device. Patients will do a brief demonstration of how to use the device in order to ensure patient understanding and proper utilization.

Follow up visit at four weeks: This is the standard follow-up appointment to discuss efficacy and

safety of the stimulator. The Vibrect device is the patient's to keep, however if they are not interested in continuing use, then can bring the device back and it will be returned to Reflexonic by the team. The patient will fill out the IIEF-5, EHS, EDITS, and TSS forms again and will be collected from the patient by nursing staff or the investigators. Patients will have a penile examination to document any sores, lesions, or irritation.

Patients in this study will not be blinded, as we would not be able to blind patients to using a vibratory device or not, and there is only one treatment group. Patients in this study will not be compared to a non-treatment group. This is a phase I trial exploring safety of the device, and we therefore want all participants to use the device and provide their individual reports and feedback.

The standard of care for men presenting with mild-to-moderate ED and requesting treatment are PDE5-inhibitors (Viagra, Levitra, Cialis). While on study, patients will be able to use on-demand PDE5-inhibitors as per usual. Future studies may compare Vibrect to PDE5-inhibitors, but the present study is exploring safety of the device.

Patients would be considered a treatment failure if they are unable to use the Vibrect device as recommended for the trial due to either mechanical issues or inability to tolerate the penile sensation when using the device.

Once given the Vibrect device, it will be the participants to keep. Should the patient not want to possess the device, they will be instructed to bring the device back at their follow-up appointment and it will be returned to the manufacturing company. Patients are able to continue using the Vibrect device for personal use after the study is complete. Patients are still required to follow the instructions in regards to duration of use and technique of application.

3. Inclusion/Exclusion Criteria

i. Inclusion criteria:

- Men ages between 30-70 interested in treatment for erectile dysfunction
- IIEF-5 score equal to or greater than 13 but less than 25.

ii. Exclusion criteria:

- Men with neurological disease, including a history of spinal cord injury or trauma
- IIEF-5 score less than 13
- History of priapism
- Men with a history of radical prostatectomy within the past 2 years.
- Pre-existing penile skin lesions/ulcers
- Allergy to latex
- Inability to understand and demonstrate device use instructions.
- Patients with insulin-dependent diabetes who suffer peripheral neuropathy or other diabetes associated complications
- Patient unwilling to engage in sexual activity
- Patient is currently participating in another clinical investigation that would serve as a contraindication to applying a stimulatory device to augment erectile function

4. DRUGS/SUBSTANCES/DEVICES

The Vibrect penile vibratory stimulation system is a medical device cleared by the

[figure not shown]
[figure not shown]
Food and Drug Administration (510k Clearance Letter attached). The FDA statement reads: "The Vibrect is a medical device indicated to provoke erection in men who experience erectile dysfunction and to provoke ejaculation in spinal cord injured men." It is currently cleared for sale with, and without a doctor's prescription.

[figure not shown]
[figure not shown]
The Vibrect is a class II medical device that is easy-to-use and when properly applied, stimulates the nerves of the penis, as a form of sexual aid. In addition, the vibratory mechanism stimulates the spinal nerve reflexes that are responsible for the initiation of penile erection and rigidity. The device is powered by a rechargeable battery. This device has two gentle vibrating motors that allows for simultaneous vibratory stimulation of both surfaces of the penis. The dorsal and ventral side of the male penis is supplied by the dorsal nerve and perineal nerve, respectively. Simultaneous stimulation of both nerves should increase the sexual response.

b. Justification and safety information if FDA approved drugs will be administered for non-FDA approved indications or if doses or routes of administration or participant populations are changed. NA

[figure not shown]
c. Justification and safety information if non-FDA approved drugs without an IND# will be administered. NA

d. For IND/IDE studies, a summary of preclinical and early human studies. NA

device open

device closed

5. STUDY STATISTICS

a. *Primary outcome variable.*

The primary outcome parameter is safety, patient tolerability, and patient satisfaction with the hand-held penile vibratory system.

b. *Secondary outcome variables.*

The secondary outcome parameter is erectile response (erection, rigidity, orgasm) and subjective patient and/or partner sexual satisfaction, when applicable.

c. *Statistical plan including sample size justification and interim data analysis.*

This is a prospective study. Descriptive statistics will be performed based on pre-treatment and post-treatment responses to validated sexual function questionnaires. This data will be utilized to perform power analyses to generate future studies. We will recruit a total of **20 patients** for this study.

d. *Early stopping rules.*

Patients who stop the use of the Viberec early, will be recorded and their reasoning will be documented. Since this is a phase I trial, patient safety and satisfaction is the primary outcome and therefore it will be essential to understand why a patient stops use prematurely.

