COVER PAGE

NCT number: 01715571

Official Title: Assessment of Penile Vibratory Stimulation
Using the Viberect in Men with Mild-Moderate ED

Document date: 5/7/2021

Principal Investigator: [name]

Participating Site: Johns Hopkins University, Baltimore,
MD, USA

Statistical Analysis Plan (SAP)

This was a pilot study and there were no data to suggest the magnitude of the effect of Viberect on ED, we performed power calculations for various scenarios of change in IIEF. The scenarios used a pattern of means with an absolute increase from pre-treatment to 4 weeks of 4 units for IIEF, and plausible conservative (higher than expected) values for the within-subject standard deviation that were increased until power fell below 80%. For IIEF, we evaluated power if the pre-treatment mean was the midpoint of the range of values eligible for study: IIEF = 18 (range 11-25). However, the power was not sensitive to the pre-treatment mean, and showed little variation according to the specific changes in mean score between time points, for a fixed overall change from pre-treatment to 4 weeks. The table below shows power to detect a 4 unit increase in IIEF with 20 patients evaluated at 4 time points, $\alpha = 0.05$, within-subject standard deviation and autocorrelation both constant over time. Power calculations were performed using PASS v. 11 (NCSS Software, Inc., Kaysville, UT), according to the method of Mueller (Mueller 1989).

Pattern of means over 4 time points		Within-subject SD	Power
Pre-test	4 weeks		
IIEF			
18	20	2	>0.99
18	20	3.5	0.88
18	20	3.8	0.81

Thus, despite the small size of the study, power is likely to be more than adequate to detect the minimum changes in IIEF (increase 4 units) considered clinically relevant.

Should a measurable positive effect be noted, a more extensive randomized, placebo controlled, blinded and possibly multi-institutional trial be considered. The information obtained from the pilot study a help guide future studies if appropriate.

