Pre-treatment IIEF, EHS, EDITS, and TSS scores was planning to be compared to post-treatment scores at 4 weeks. The primary analysis for all scores were repeated measures analysis of variance (RM ANOVA); if there are no missing time points, otherwise, a mixed model was used. The primary endpoint was the TIME effect, i.e. to test for a change from pre-treatment value of IIEF, EHS, EDITS, or TSS. The minimum change considered clinically relevant was an increase in IIEF and EDITS of 4 units and EDITS of 4 units. In addition to absolute change in IIEF or EDITS scores, we evaluated models of percentage change from pre-treatment value. If the overall effect of TIME is statistically significant, we used paired t-tests comparing pre-treatment to

each of the post-treatment values, with a Bonferroni p-value adjustment, to determine the time at which an increase in IIEF and EDITS of at least 4 points can first be detected. Covariates to be evaluated as potential confounding factors include age, comorbidity or cause of ED, body mass index, and other medications.

Data were analyzed using GraphPad Prism ver. 8 (GraphPad Software, San Diego, CA, USA). A P value $<.05$ was considered statistically significant.

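### The protocol plans descriptive questionnaire summaries to feed later power analyses; the SAP makes a hypothesis test at P<.05 the primary analysis, the two are not reconciled, and P<.05 would not show the SAP's own 4-unit relevant change

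*Protocol*

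**What the plan says.** **Protocol, section 5 (Study Statistics), item c.** For the questionnaires: "Descriptive statistics will be performed based on pre-treatment and post-treatment responses to validated sexual function questionnaires". The stated use is: "This data will be utilized to perform power analyses to generate future studies". Item c fixes the sample at 20 and gives no hypothesis, test, alpha or power. Section 2 (Study Procedures) adds, for the week-4 questionnaires: "The answers to these validated questionnaires will be compared to baseline to evaluate patient effect when using the device". It names no method for that comparison.

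**Protocol, section 5, items a and b.** "The primary outcome parameter is safety, patient tolerability, and patient satisfaction with the hand-held penile vibratory system". "The secondary outcome parameter is erectile response (erection, rigidity, orgasm) and subjective patient and/or partner sexual satisfaction, when applicable".

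**SAP, analysis paragraphs.** "The primary analysis for all scores were repeated measures analysis of variance (RM ANOVA"), with a mixed model if time points are missing. The primary endpoint is the time effect on IIEF, EHS, EDITS or TSS. Bonferroni-adjusted paired t-tests follow if that effect is significant. Models of percentage change and several covariates are added. The minimum relevant change is 4 units for IIEF and EDITS. The closing lines say "Data were analyzed using GraphPad Prism ver. 8" and set P<.05 as the significance threshold.

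**SAP, opening and power table.** The text begins "This was a pilot study and there were no data to suggest the magnitude of the effect of Viberect on ED". It then gives power for 20 patients at 4 time points and concludes that power is more than adequate for a 4-unit IIEF increase.

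**The concern.** The two documents describe different kinds of inference. In the protocol, the questionnaire data are summarised so that power can be worked out for a later study. In the SAP, the same data carry a primary hypothesis test with a significance level and a claim of adequate power now. A SAP may add detail to a protocol, but this one changes the role of the result and does not say so.

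Two things are at stake. First, a P value below .05 would be read as the planned main finding. The study has one arm and no blinding, and it allows on-demand PDE-5 inhibitors, so a change over time cannot be attributed to the device on that evidence. Second, the next study needs the size of the change, its SD and its uncertainty. The SAP asks for no confidence interval, and a test against zero change does not say whether a change of 4 units was reached.

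**Working it through.** **Step 1: the texts side by side.**

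| Item | Protocol section 5 | SAP |
|---|---|---|
| Questionnaire analysis | Descriptive, before and after | RM ANOVA or mixed model, then paired t-tests |
| Significance level | None | .05 |
| Power | For future studies | Claimed adequate for this one |
| Primary | Safety, tolerability, satisfaction | Time effect on IIEF, EHS, EDITS or TSS |
| Erectile response | Secondary | IIEF and EHS share the primary role |

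No passage in either document bridges the columns.

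**Step 2: reproduce the SAP's power.** The SAP states >0.99, 0.88 and 0.81 at within-subject SD 2, 3.5 and 3.8 (n = 20, k = 4 time points, alpha 0.05). For one-group RM ANOVA the noncentrality is λ = n·Σ(mean_j − grand mean)² / [SD²(1 − ρ)], with k − 1 = 3 and (n − 1)(k − 1) = 57 degrees of freedom. The SAP gives neither the intermediate means nor the autocorrelation ρ, so both are assumed.

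- Means 18, 20, 21, 22 (a 4-unit rise), ρ = 0: the sum of squares is 8.75. At SD 3.5, λ = 20 × 8.75 / 12.25 = 14.3 and power is 0.880. At SD 3.8, λ = 175 / 14.44 = 12.1 and power is 0.816. At SD 2, power is >0.99.
- A linear 4-unit rise with ρ = 0 gives >0.99, 0.885 and 0.823.
- The means as printed in the table, 18 to 20, give 0.28 to 0.41 at SD 3.5 and 0.24 to 0.35 at SD 3.8 with ρ = 0. They reach the stated power only if ρ is about 0.65 to 0.77.

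The stated power is thus reproduced for a 4-unit rise with ρ = 0.

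**Step 3: what P<.05 would show.** The protocol has two visits, baseline and week 4. With two time points RM ANOVA is a paired t-test, so the smallest mean rise reaching P<.05 equals the half-width of the 95% CI:

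half-width = t(0.975, 19) × SD × √[2(1 − ρ)] / √20, with t = 2.093 and √20 = 4.472.

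Assumptions: two-sided testing (the SAP does not state sidedness), 20 complete pairs, and an observed SD equal to the planning SD.

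| Within-subject SD | ρ (assumed) | SD of change | Half-width |
|---|---|---|---|
| 2 | 0 | 2.83 | 1.3 |
| 3.5 | 0 | 4.95 | 2.3 |
| 3.8 | 0 | 5.37 | 2.5 |
| 3.5 | 0.5 | 3.50 | 1.6 |
| 3.8 | 0.5 | 3.80 | 1.8 |

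With ρ of 0.65 to 0.77, as the printed means would need, the half-width at SD 3.5 to 3.8 is about 1.1 (3.5 × √0.46 × 0.468) to 1.5 (3.8 × √0.70 × 0.468).

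**Step 4: set this against 4 units.** Every value in Step 3 is below 4. At SD 3.5 and ρ = 0.5, a mean rise of 1.64 would be just significant, with a 95% CI from 0 to 3.28 that lies wholly below the relevant change. At SD 3.8 and ρ = 0, a just-significant rise of 2.5 has an interval from 0 to 5.0, which includes 4. The P value is the same in both cases, but the intervals support different conclusions.

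**The case against.** Several stronger readings are tempting, and the documents do not support them.

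- **That the protocol permits descriptive statistics only.** It does not exclude tests, and section 2 plans a comparison with baseline. The SAP can fairly be said to supply a method for that comparison.
- **That the SAP claims a confirmatory result.** It does not use the word. It calls the study a pilot and says a positive effect would lead to considering a larger randomized, blinded trial, which fits the protocol's purpose.
- **That the tests were added after the protocol or after the data were seen.** The protocol text provided carries no date. The SAP is dated 5/7/2021 and mixes past and future tenses. The order of the decisions cannot be established.
- **That the SAP estimates nothing.** It does evaluate absolute and percentage change and sets a relevance threshold. What is clearly missing is the confidence interval.

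It can also be said that the interval width would be the same if the documents agreed. The SAP calls its SDs conservative, and its SD 2 row gives a narrower interval. That is correct. The width does not measure the conflict; it shows what a P value alone would leave out, and the SD 2 row brings the significance boundary further below 4 units.

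Finally, the change of primary outcome is arguably the larger conflict. That too is fair, and the fix must not make it worse by putting questionnaire change ahead of safety.

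What remains is that the SAP's primary analysis, primary endpoint, alpha and power claim present the test as the planned main result, and the protocol's statistical plan contains none of these.

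**Conclusion.** The concern holds as a conflict over the type and standing of the questionnaire analysis. Protocol section 5 item c describes summaries for future planning. The SAP makes a test at P<.05 primary and does not reconcile the two. A significant result would be presented as a pre-planned primary finding from 20 unblinded men without a control group. A reader might infer a post hoc or confirmatory claim; the documents show neither.

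The practical size is the gap between significance and relevance on the IIEF. Mean rises of about 1.6 to 2.5 units (SD 3.5 to 3.8, autocorrelation 0.5 to 0), or 1.3 units at SD 2 with autocorrelation 0, would reach P<.05 against a relevance threshold of 4. These figures depend on the assumed autocorrelation, on 20 complete pairs and on two-sided testing. They apply to the IIEF alone, because the SAP gives no SD for EDITS, EHS or TSS. The textual conflict depends on none of them.

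**What to change.** In the SAP:

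1. For each score, report the mean (SD) at baseline and week 4, and the mean paired change with its SD and 95% CI. Read the IIEF and EDITS intervals against the 4-unit threshold.
2. Keep the protocol's order of outcomes: safety, tolerability and satisfaction primary, erectile response secondary.
3. Label the RM ANOVA or mixed model, the paired t-tests, and the percentage-change and covariate models as exploratory analyses not specified in protocol section 5 item c. State when they were specified relative to data access.

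The cost is some SAP wording and one simple table; no new data are needed. The downside for the sponsor is that a significant P value can no longer be called the primary result.

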6. RISKS

a. *Medical risks, listing all procedures, their major and minor risks and expected frequency.*

Definition of adverse events: Adverse events related to the use of the Viberec device include any user discomfort during or after use of the device, including pain, fatigue, numbness, rash, or device malfunction.

Potential (anticipated) adverse events

-Pain, numbness of the penis or the hand holding the device

Adverse event reporting

i. Description of adverse events (see risk analysis)

ii. Serious adverse events

-potential serious adverse events include device malfunction, vibrating pad dislodgment and vibrating tip damaging the penis.

iii. Unanticipated adverse device effects

- Device overheats and burns. The device will not be used while connected to the electric outlet, therefore minimizing potential risk of burns or overheat

iv. Adverse event severity/strength: To be reported immediately to senior investigator and principal investigator.

v. Serious adverse event narratives: reports and narratives will be included

b. *Time periods for adverse events reporting:*

Weekly reporting to senior and principal investigator.

Risk	Occurrence Potential	Mitigation
Inability to correctly use the Viberect device according to User's Guide.	Mild	Detailed and Simplistic (with figures) instructions are included in the in the User's Guide. Also the manufacturer recommends in the User's Manual that the user perform the Viberect method for at least two occasions in a clinical setting before using at home.
Any user discomfort during or after use of the device, including pain, fatigue, numbness, rash, device malfunction or hand pain from holding the device.		Viberect Device must not be used more than 10 minutes per day with strict accordance to the User's manual. Also, manual includes A WARNING that states: "Vibratory stimulation may cause a superficial trauma to the skin resulting in bruising, bleeding or superficial ulceration. If any such condition occurs, refrain from vibrating and consult your physician. This device should not be used over swollen or inflamed areas or skin eruptions."
User does not respond to device.		User's Guide provides direction that the Viberect may have to be used multiple times before it is effective. Not all men will responds to this treatment.
Skin irritation, tear, or infection	Moderate	As specified in the User's Manual, the Viberect Device should not be used if visible penile skin irritation (e.g., swollen or inflamed areas or skin eruptions). Also, User's Guide warns that "Vibratory stimulation may cause a superficial trauma to the skin resulting in bruising, bleeding or superficial ulceration. If any such condition occurs, refrain from vibrating and consult your physician." The device should not be used for more than 10 minutes a day.
Serious Medical Conditions Such as Priapism.	Serious	If the user develops an erection that lasts for more than four hours, he may have developed priapism, which is a medical/surgical emergency. Contact your physician immediately or go to the emergency room for timely treatment.

Device malfunction, vibrating pad dislodgment and vibrating tip damaging the penis.	Device malfunction	As specified in the User's Manual the Viberect device should not be used over swollen or inflamed areas or skin eruptions. Also, the User's Guide will advise user to:  check the surface of the pad over-mold for any signs of wear/degradation and replace if needed; and  check the integrity of the pad-pad over-mold assembly.
Device overheats and burns.		The circuitry/power source is electrically isolated from the patient's skin by thick plastic cover; that is, no circuitry or electrical components are exposed to the skin. In addition, no conductible metallic components of the device are exposed to the outside.
Use of Device while Charging		User Manual specifies not to use the device while charging and connected to an electrical outlet.

Legal risks such as the risks that would be associated with breach of confidentiality.

All data collection and will be secured to assure confidentiality and the study database will be stored in encrypted database that is only available to senior and principal investigator or research coordinator who is responsible for data collection.

Financial risks to the participants.

There is no financial risk to the patient. The Viberect device will be provided for free to each participant. Clinic visits will be billed to the participant's insurance company as a consultation and a standard-of-care follow-up appointment. If the participant does not have insurance coverage for specialist appointments, they will be responsible for paying for their visits out-of-pocket. The study does not offer financial compensation, however the Viberect device will be provided for free to the participant.

Steps taken to minimize the risks.

A comprehensive user manual will be provided to each study subject, and detailed person

to person instructions will be given to them prior to enrolling in the study. A demonstration will be provided prior to the patient using the device independently to ensure they have a full understanding of how to use the device.

Plan for reporting adverse events unanticipated problems or study deviations.

The occurrence of any serious adverse effects will end the patient's participation in the study and halt enrollment in the study to determine the safety of continuing. Each and every possible adverse effect of Viberec will be investigated and treated individually to minimize the participant's discomfort. The safety of having the individual complete the study will also be assessed on an individual basis. At any time the participant can decide to terminate his participation in the study and no penalty or loss of benefits to which they are entitled.

7. Confidentiality

Paper consent forms, enrollment check sheets, and other source or study documentation will be kept in a study binder. This binder will be stored in a locked office available only to the study team. Electronic data will be housed in a secure password protected database maintained by the Data Informatics Services Core within the Johns Hopkins Biostatistics Center. Only the study team will have access to this secure database. To maintain the protected information of patients enrolled in this study, only the study Principal Investigator and primary coordinators will have the ability to export data containing identifying information from this master database. For the purposes of analysis, only de-identified data will be exported.

8. Benefits

i. Individual participant

The patient's erectile function and sexual satisfaction may improve as a result of participation in this study. However, there is no guarantee of this. The information from this research study may lead to a better treatment in the future for people with erectile dysfunction. The patients may not benefit from participation in this study. Their conditions may not get better or but it unlikely to become worse while they are in this study. The study does not offer financial compensation, however the Viberec device will be provided for free to the participant.

ii. Society

Erectile dysfunction is a highly prevalent medical and psychological condition that affects millions of men worldwide and is associated with a significant reduction in overall quality of life. The results of this study can lead to further investigations that can show the efficacy of this safe modality in the management of erectile dysfunction.

9. Payment and Remuneration

The study does not offer financial compensation, however the Viberec device will be provided for free to the participant.

10. Costs

The Viberec device will be provided to patients free of charge. There are no anticipated costs outside of the usual standard of care for patients with erectile dysfunction. Participants will be seen routinely in clinic as a standard part of their care plan. If patients decide to use PDE5 inhibitors (such as Viagra, Cialis, or Levitra) in addition to their use of Viberec, they will be responsible for the cost of this drug, as per usual.

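### Safety and tolerability are part of the primary outcome, but the listed diary items include no adverse event term and nothing is scheduled between baseline and about week 4

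*Protocol*

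**What the plan says.** **Outcome.** Protocol section 5a names safety, tolerability and satisfaction as the primary outcome, in 20 men.

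**Diary.** Section 2 (Study Procedures) says: "Men will record the frequency of device use, erectile response with stimulation, and whether they were able to achieve sexual satisfaction". Use of PDE-5 inhibitors is to be recorded separately. The same section then says: "The diaries will be evaluated to explore both the safety, as well as the patient effect when using the Viberec device".

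**Visits.** Section 2b says: "A total of 2 clinic visits will be included in this study". These are baseline and "a follow-up visit approximately 4 weeks after initiation of study period". At the second visit safety is discussed and "Patients will have a penile examination to document any sores, lesions, or irritation".

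**Adverse events.** Section 6a defines device-related adverse events as user discomfort during or after use, and names pain, numbness, fatigue, rash and device malfunction. Device malfunction is listed again among the potential serious events.

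**Reporting.** Section 6a(iv), on severity, says: "To be reported immediately to senior investigator and principal investigator". Section 6b, on time periods, says: "Weekly reporting to senior and principal investigator". Neither says which events it covers. The reporting plan at the end of section 6 says that any serious adverse effect ends the man's participation and will "halt enrollment in the study to determine the safety of continuing".

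**The concern.** The protocol gives the diary a safety purpose, but the recording instruction contains nothing that would serve it. Followed as written, short-lived pain, numbness, fatigue or a passing malfunction has no listed source at the time it happens. It reaches the data only if the man volunteers it or remembers it at about week 4.

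This bears on the primary outcome. The study has a single arm and no comparison group, so the event rate itself is the result. If the rate is too low because events were not asked about, nothing in the design would reveal that. Section 5c says the data will feed the planning of later studies, so an under-count could carry forward.

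**Working it through.** The plan states no figure on this point that could be reproduced. The check compares its sections, with simple arithmetic on exposure.

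**1. Diary items against adverse event terms.** Section 2 lists three items: frequency of use, erectile response and sexual satisfaction (PDE-5 inhibitor use is kept separately). Section 6a names five terms: pain, numbness, fatigue, rash and device malfunction. The overlap is 0 of 5.

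**2. Scheduled contacts between the visits.** Two visits in total, less one at baseline and one at about week 4: 2 − 1 − 1 = 0. Neither document describes a call, a message or a diary return in between.

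**3. Exposure before the first planned safety check.** Section 2 asks for at least 3 sessions a week over four weeks and allows one a day.
- Minimum: 3 × 4 = 12 sessions.
- Maximum: 1 × 28 = about 28 sessions (slightly fewer in practice, since sessions must be more than 24 hours apart).

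An event that is not volunteered can stay unknown for up to about 28 days.

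**4. What the week-4 visit can find by itself.** The examination looks for sores, lesions and irritation. Of the five terms, only rash is plausibly visible, and only if it has not cleared. The other 5 − 1 = 4 depend on what the man says. Section 5c describes the questionnaires as sexual function instruments, not adverse event instruments.

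**5. Direction and size of the error.** Let p be the true proportion of men with a transient event, v the share of those men who volunteer it before week 4, and r the share of the rest who recall it at week 4. Ignoring false reports:

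recorded proportion = p × [v + (1 − v) × r]

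This equals p only if v = 1 or r = 1, and is otherwise smaller. The documents give no value for p, v or r. The direction follows from the design, but the size does not.

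**6. Whether the SAP fills the gap.** Its power paragraph assumes four time points, which might suggest interim contacts. It gives no dates for them, the protocol schedules two visits, and the scores the SAP analyses are IIEF, EHS, EDITS and TSS. None of these records adverse events.

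**The case against.** **The diary form is not in the documents.** Section 2 does not call its list complete, and it names the diary as a safety source. A reader might infer that the diary does not ask about adverse events. That goes too far. What can be said is that the listed items omit them and that no return before week 4 is stated. If the form already carries such items, the fix shrinks to a wording change.

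**The two reporting times can coexist.** A reader might infer that immediate and weekly reporting contradict each other. They need not: prompt notice of some events plus a weekly summary is an ordinary arrangement. Both rules govern onward reporting to the investigators, not reporting by participants. A study-level weekly report could also draw on the week-4 visits of men enrolled earlier. The remaining defect is that the split is undefined.

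**The halt can operate.** A reader might infer that neither the reporting times nor the enrolment halt can work. An event that a man volunteers can be passed on at once, enter the weekly report and trigger the halt. Serious events are the least likely to go unmentioned for four weeks, and the risk table tells a man with priapism to seek care at once. The weak spot is systematic capture of minor, transient events.

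**Contact instructions may exist elsewhere.** The consent form, contact pages and user manual are not in the available text, so the lack of a stated telephone route does not count against the plan. The absence of a scheduled interim visit does stand.

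**Other tolerability capture exists.** Section 5d requires early stops and their reasons to be documented, and section 2b defines treatment failure by mechanical trouble or not tolerating the sensation. Both help. Neither covers a man who has a transient event and carries on.

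**Conclusion.** The point holds as a gap in how a primary outcome is ascertained. The protocol's listed diary items contain 0 of its 5 adverse event terms, and no contact or diary return is scheduled over 12 to about 28 sessions. Transient events that are not volunteered would rest on recall at about week 4, which tends to under-count them.

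This assumes that the diary follows the list in section 2 and that recall over four weeks is incomplete. Putting a number on the bias, for example a given true rate halved, would need an event rate and a recall rate that the documents do not supply, so none is claimed.

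Two wording problems are secondary: the undefined split between immediate and weekly reporting, and device malfunction appearing as both a general and a serious event, which leaves the trigger for the halt unclear. The change should be made. The finding does not show that the safety procedures are unworkable.

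**What to change.** **Main change.** In Protocol section 2, add to each diary session entry a yes/no with severity for the five terms in section 6a: pain, numbness, fatigue, rash and device malfunction. State in section 5 that these entries are the source for the primary safety and tolerability summary.

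**Cost.** One extra diary line per session, so 20 × 12 = 240 to about 20 × 28 = 560 lines across the study. The burden on each man rises slightly, and the observed event rate will probably be higher.

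**Wording.** State in 6a(iv) and 6b which events are reported immediately and which weekly. Reconcile the two listings of device malfunction with each other and with the enrolment halt. The choice of rule is for the sponsor.

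**Optional.** Remote diary collection at weeks 1, 2 and 3 would shorten the delay, at 3 × 20 = 60 short contacts. The main change does not depend on it.

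**If data collection is over.** The SAP is written partly in the past tense. In that case the report should describe how adverse events were elicited, attach the diary form, and qualify the rates accordingly.
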